PILOT LIPID MRI STUDY PROTOCOL AND STATISTICAL ANALYSIS

OFFICIAL TITLE: TRIGLYCERIDE EFFECTS ON BLOOD FLOW IN THE HUMAN BRAIN

NCT: NCT05218018

DATE: 01 – JAN - 2020

PILOT LIPID MRI STUDY PROTOCOL AND STATISTICAL ANALYSIS

Rationale:

Overview: High fat feeding (HFF) is a risk factor for Alzheimer's disease (AD), but this risk factor is modulated by APOE genotype. Acute meal studies including lipid tolerance tests are increasingly being used to understand mechanisms by which diet affects disease processes. We have consistently shown that E4 carriers respond differently to HFF in acute meal challenges; we wish to further explore this phenomenon in older adults by assessing cerebral blood flow (CBF), given its tight coupling to brain metabolism. Here we propose to use arterial spin labeling (ASL) MRI as this non-invasive imaging technique can detect small changes in global and regional CBF, and acute Δ CBF in response to glucose, insulin and mixed meals have been demonstrated in humans. Project objectives: 1. To determine which time point (1, 2, or 3 hours) produces the most robust Δ CBF after ingestion of a lipid drink in 30 older adults. 2. To determine which regions of the brain respond to HFF. 3. To determine whether E4 status influences Δ CBF to lipid ingestion at the global or regional level.

Procedure:

Overview: Participants (n=30) will be recruited from Seattle-based registries. Participants will arrive at the South Lake Union UW translational research unit (TRU) in a fasting state and after giving informed consent they will undergo the first ASL MRI image acquisition. Then they will drink the lipid product (just under half a cup of heavy whipping cream) and undergo 3 more acquisition scans at 1, 2, and 3 hours post drink. They will then be offered lunch for purchase at the UW cafeteria and discharged home.

Participants: All study procedures will be submitted to the UW Institutional Review Board for approval before any participants are recruited; IRB application for this project has been started and will be submitted by October 22, 2019. We maintain a database from the Meal and Memory study which contains over 50 participants, several of whom know their APOE genotype. Inclusion criteria are age 55 and older, and able to read English, give informed consent, undergo MRI and ingest dairy products. For the study visit, participants will be asked to fast for 8 hours. They will undergo informed consent, and then the protocol will begin: First a 30 minute ASL protocol will be run, then the participant will be given the heavy cream to drink over 5 minutes (100 mls just under $\frac{1}{2}$ cup; 370 calories, 40.4 grams of total fat, 23.6 grams of saturated fat). Participants will then undergo 3 more 15-minute scans at 1, 2, and 3 hours post drink. After the last MRI image acquisition, lunch will be offered, participants will receive a gift card, and be discharged.

MRI protocol: For the ASL protocol, we will use pseudo-continuous arterial spin labeling to measure CBF in ml/100g/min as a marker of perfusion for improved signal quality. In this approach, magnetically labeled arterial blood water serves as the endogenous contrast. Experiment: As per the consensus recommendations, we will use a sequence (5.5 minutes) with long label duration = 1.8 s, long post-labeling delay = 2 s, with labeling offset = 25-30 mm, slices = 20, spatial resolution = $3.5 \times 3.5 \times 5$ mm³, field of view = $240 \times 240 \times 100$ mm³, SENSE-factor = 2, TR/TE= 5000/18 ms. We will apply dual adiabatic background suppression pulses to minimize gray and white matter tissue contamination at TI = 2.05 and 3.25 s. Finally, we will acquire an equilibrium magnetization scan (M0, 1 minute), identical to the above scan, but with TR = 10,000 ms and no labeling or background suppression.

Analysis: Analysis will be done under the supervision of [name] and [name] with the UW Diagnostic Imaging Sciences Center (DISC). We will first apply motion correction to the arterial spin labeling images using FSL-MCFLIRT and register them to the M0 image. Then, we will perform a pair-wise subtraction between the control and null images and apply a two-compartment model to quantify CBF. We will co-register the resulting CBF map to the T1 scan followed by a transformation to MNI space. The temporal regions such as the entorhinal cortex, temporal lobe, hippocampus as well as the posterior cingulate and lateral parietal lobules will be identified using standard Harvard-Oxford Cortical and Subcortical atlas. CBF values will be compared in these regions between the 3 groups. The region of interest approach can dilute effects that are smaller than the size of the region of interest. Therefore, we will also perform permutations testing in FSL to evaluate voxel-wise CBF differences between group. In order to ensure that the voxel-wise outcomes are not mere chance, we will impose strict family-wise error correction for multiple comparisons. Blood flow data will be standardized to ml/100g/min, as per ASL protocols.

Statistics: From these images we will obtain measures on global blood flow (ml/100g/min) as well as regional blood flow in pre-defined regions (i.e. right temporal lobe). We will utilize standard statistical models to compare the 1, 2, 3, hour ASL to the baseline ASL to ascertain what time point produces the most robust change result. This will help cut down on the signal-to-noise ratio of the data as participants will serve as their

own control, in a repeated measures design. We will also compare total and regional Δ CBF by E4 status to detect whether patterns are different between E4 carriers and non-carriers (treatment*E4 effect).

Summary: Data from our laboratory consistently identifies that E4 carriers, who are at higher risk for AD, show paradoxical improvement after high fat feeding. We wish to explore this finding further using state-of-the-art MRI imaging to assess blood flow pattern responses in E4 carrier and non-carrier groups. With this project we will determine the most optimal time point for detecting post-lipid Δ CBF, as well as determine which regions of the brain respond to HFF and whether any regions differ by E4 status. With these types of studies, we hope to gain a more in-depth understanding of how HFF exerts influence on brain function and metabolism.

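### The Analysis section compares three groups that the design does not contain, and leaves the voxel-wise test with no contrast against baseline

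*Combined protocol and SAP*

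**What the plan says.** The Procedure section describes one cohort of 30 people. All take the same drink, and each is scanned at baseline and at 1, 2 and 3 hours afterwards. The only factor that divides participants is E4 status, which the Statistics and Summary sections treat as carrier versus non-carrier.

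The Analysis section states the regional comparison as "CBF values will be compared in these regions between the 3 groups". It then explains why a second analysis is needed: "The region of interest approach can dilute effects that are smaller than the size of the region of interest". That analysis is given as "we will also perform permutations testing in FSL to evaluate voxel-wise CBF differences between group", and for it "we will impose strict family-wise error correction for multiple comparisons".

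The Statistics section, which names only global flow and flow in pre-defined regions, sets out different comparisons: "We will utilize standard statistical models to compare the 1, 2, 3, hour ASL to the baseline ASL", with each participant as his or her own control, and "We will also compare total and regional Δ CBF by E4 status".

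Two of the project objectives bear on this: "To determine which regions of the brain respond to HFF" and "To determine whether E4 status influences Δ CBF to lipid ingestion at the global or regional level".

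**The concern.** A comparison of three groups cannot be set up from this design, and it does not agree with the Statistics section. For the regions, a reader can fall back on that section. For the voxel-wise test there is nothing to fall back on: the document does not say which groups are compared, whether the maps are CBF or change in CBF, or which scan is used. The analyst would have to choose the design matrix, possibly after seeing the data.

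The voxel-wise test is there to catch effects too small to show in a regional average. If it is run on CBF between E4 groups, two things go wrong. A response to the drink that both groups share is invisible to it. A difference between carriers and non-carriers that existed before the drink can be read as a difference in response to it.

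**Working it through.** **1. Levels of each factor**

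| Factor | Levels | Source |
|---|---|---|
| Treatment arm | 1 (all take the same drink) | Procedure |
| Scan time, within person | 4 (baseline, 1, 2, 3 h) | Procedure |
| E4 status, between persons | 2 | Statistics, Summary |

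No grouping of participants has three levels. The word group (or groups) occurs three times: twice undefined in the Analysis section, and once in the Summary, where it means E4 carriers and non-carriers. The only three in the design is the set of post-drink scans, which are repeated measures on the same people.

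**2. Comparisons stated for each type of measure**

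| Measure | Post-drink versus baseline | Δ CBF by E4 status |
|---|---|---|
| Global CBF | yes, Statistics | yes, Statistics |
| Regional CBF | yes, Statistics | yes, Statistics |
| Voxel-wise CBF | not stated | not stated; only CBF between groups |

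**3. What a between-E4 test of CBF estimates.** Let non-carriers have baseline mean m, carriers m + d, and let both respond by r.

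- Post-drink difference: (m + d + r) − (m + r) = d. The response r cancels, so it cannot be detected, whatever its size.
- Difference in Δ CBF: r − r = 0, which is the correct answer for the E4 question.
- If d = 0 as well, the post-drink test rejects only at its false-positive rate.

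**4. Size of the baseline problem (illustrative).** The plan gives no figure to reproduce: n = 30 is stated without SD, effect size, alpha or power. Assumptions not in the documents: E4 splits of 15/15, 10/20 and 8/22; baseline differences d of 0.2, 0.5 and 0.8 SD; identical responses; one voxel; two-sided 5% before family-wise correction.

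The two-sample t test has 28 df, critical value 2.048 and noncentrality d / √(1/n₁ + 1/n₂). For 15/15 and d = 0.5 this is 0.5 / 0.365 = 1.37, which gives a rejection rate of 0.262.

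| d (SD) | 15/15 | 10/20 | 8/22 |
|---|---|---|---|
| 0.2 | 0.083 | 0.079 | 0.075 |
| 0.5 | 0.262 | 0.239 | 0.216 |
| 0.8 | 0.562 | 0.514 | 0.465 |

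These rates do not depend on the correlation between scans. A simulation (20,000 replicates per cell; correlations 0.3, 0.5 and 0.8; all three splits) gave 0.073 to 0.088, 0.212 to 0.266 and 0.468 to 0.565 on post-drink CBF. On Δ CBF it gave 0.046 to 0.054 in all 27 cells.

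**5. Power is not the argument.** Suppose there is no baseline difference, variance is equal at each scan and the scan-to-scan correlation is ρ. Then Var(Δ) = 2σ²(1 − ρ), so the noncentrality on post-drink CBF is √(2(1 − ρ)) times that on Δ CBF. Take an E4 difference with 80% power on Δ CBF (noncentrality 2.902):

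| ρ | 0.2 | 0.3 | 0.4 | 0.5 | 0.6 | 0.7 | 0.8 | 0.9 |
|---|---|---|---|---|---|---|---|---|
| Power on post-drink CBF | 0.943 | 0.912 | 0.866 | 0.800 | 0.708 | 0.583 | 0.426 | 0.241 |

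Post-drink CBF has more power below ρ = 0.5 and less above it. The documents give no ρ, so the case for Δ maps rests on steps 3 and 4.

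**The case against.** **The harm depends on one reading.** The document does not fix group as E4 status in the voxel-wise sentence. The nearest antecedent is the undefined three groups, which may loosely mean each post-drink time against baseline; on that reading the voxel-wise test already has the contrast said to be missing. The Summary also speaks of responses in the E4 groups, which hints at change, and the Statistics sentence on time points is not expressly limited to regions. This stands as a caution: what is certain is that the contrast is unstated. But none of these readings is written down, and the Statistics section names only global and regional measures. A comparison of the three post-drink scans with one another would not help either. It omits baseline, so a response that is constant from 1 to 3 h would cancel.

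**The percentages do not describe the planned test.** They are for one voxel at an uncorrected 5%, with an assumed baseline difference, while the plan commits to family-wise correction. At an illustrative per-voxel threshold of 0.0001 and a 15/15 split, the rates fall to about 0.03%, 0.35% and 2.4% for 0.2, 0.5 and 0.8 SD. This is correct, and the 5%-level figures should be read only as illustration. The bias remains, however. The nominal rate at that threshold is 0.01%, so those rates are about 3, 35 and 240 times nominal, and the map-wide rate could be higher if a baseline difference is widespread. Family-wise correction guards against chance findings; it does not repair a wrong contrast.

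**Δ maps are one choice among several.** A voxel-wise repeated-measures model with a time-by-E4 term would also serve. Adjusting for baseline CBF as a covariate is less safe here, because E4 status is not assigned at random. With equal variances the within-group slope is ρ, so the adjusted E4 difference under identical responses is d − ρd = d(1 − ρ), not zero.

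**The analysis is supplementary, in a pilot of 30.** This is true, and it limits the severity.

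**Conclusion.** The concern holds. That three groups match no factor in the design, and disagree with the Statistics section, is certain from the text. For regional CBF the consequence is a wording correction. For the voxel-wise test the comparison is unspecified. With group in its only identified sense, the test misses any response common to carriers and non-carriers, and it confuses a baseline E4 difference with a difference in response. The first failure follows by algebra and needs no assumption beyond that reading. The size of the second depends on a baseline difference that the documents do not give: 7.5% to 8.3%, 22% to 26% or 47% to 56% false findings for 0.2, 0.5 or 0.8 SD, single voxel and uncorrected, against 5% on Δ CBF. The project objectives are stated at global or regional level and remain covered, so the loss is confined to the added analysis. It should be fixed before the images are analysed, but it does not threaten the study.

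**What to change.** **Regional sentence.** Replace the reference to three groups with: *Regional CBF at 1, 2 and 3 h will be compared with baseline within participant, and Δ CBF will be compared between E4 carriers and non-carriers.*

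**Voxel-wise sentence.** State that each participant's post-minus-baseline CBF maps will be computed, and that two tests will be run on them:

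- for response to the drink, a within-person permutation test of the Δ maps against zero, for example one-sample sign-flipping in FSL;
- for the E4 question, a two-sample permutation test of the Δ maps between carriers and non-carriers.

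Keep the planned family-wise error correction. Extending it across the three time points is optional, but the plan should say whether it is done.

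**Cost.** Two sentences of analysis text and a different design matrix in software already planned. No new data, scans or participants.

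### Objective 1 chooses among 1, 2 and 3 hours, but the sentence that makes the choice compares each hour only with baseline and plans no estimate of how well the hours are separated

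*Combined protocol and SAP*

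**What the plan says.** The Project objectives in the Overview set the first task as finding "which time point (1, 2, or 3 hours) produces the most robust Δ CBF after ingestion of a lipid drink in 30 older adults". The Summary repeats it as a promise: "With this project we will determine the most optimal time point for detecting post-lipid Δ CBF".

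The Statistics section is the only place that says how the hour will be chosen. Standard models, not further specified, will "compare the 1, 2, 3, hour ASL to the baseline ASL to ascertain what time point produces the most robust change result". It adds that participants act as their own controls in a repeated measures design. The data feeding the choice are "measures on global blood flow (ml/100g/min) as well as regional blood flow in pre-defined regions", and none of these measures is named as the one that decides.

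Two sentences in the Analysis section bear on the point. One says "CBF values will be compared in these regions between the 3 groups"; the three groups are not defined. The other is the only multiplicity statement, and it covers voxel-wise results: "In order to ensure that the voxel-wise outcomes are not mere chance, we will impose strict family-wise error correction for multiple comparisons".

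**The concern.** The question is comparative: which hour is best. The comparisons specified are three separate ones against a common baseline. An hour that differs clearly from baseline and one that narrowly fails to do so may hardly differ from each other, and the baseline comparisons do not reveal this. The quantities that do are the differences between hours, and the plan specifies none of them.

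Two gaps add to this. The winning criterion is not stated (largest mean change, largest change relative to its variability, or smallest p-value). Nor is it stated whether global CBF or a region decides. On their own these would be missing detail. Here they matter because different criteria or measures can name different hours, and there is no rule to settle it.

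At stake is the deliverable of objective 1, one named hour. Under this plan an hour can be named with no planned indication of whether the data distinguish it from the other two.

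**Working it through.** The documents state no alpha, effect size, SD, within-person correlation or power, so there is no figure of the plan's own to reproduce.

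**Inputs.** From the documents: n=30; scans at 0, 1, 2 and 3 h; global CBF plus five named regions. Assumed: SD of change 1 at every hour; correlation rho between hourly changes of 0.3, 0.5 or 0.7; two-sided 5% level. The middle value, 0.5, is what a shared baseline produces when scan errors are independent with equal variance. Patterns such as 0.3/0.5/0.3 below are the true changes at 1, 2 and 3 h in SD units.

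**1. What baseline comparisons can suggest when the hours are identical.** With a true change of 0.4 SD at every hour, each test has noncentrality 0.4 × √30 = 2.19 against a critical value of 2.045 (t, 29 df). Each test is therefore not far from a coin toss, and mixed results are common. By simulation, some but not all hours reach p<0.05 in about 39 to 61% of trials (rho 0.7 down to 0.3). A direct test of equal hours also rejects in only 8 to 9% of those trials.

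**2. What a direct comparison gives.** The SD of an hour-versus-hour difference is √(2(1 − rho)), and the 95% CI half-width is 2.045 × √(2(1 − rho)) / √30.

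| rho | SD of difference | 95% CI half-width | Difference giving 80% power (0.529 × SD) |
|---|---|---|---|
| 0.3 | 1.18 | 0.44 | 0.63 |
| 0.5 | 1.00 | 0.37 | 0.53 |
| 0.7 | 0.77 | 0.29 | 0.41 |

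The intervals are wide. That is information the reader of a pilot needs.

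**3. How well ranking works, and how often the winner is separated.** The second column spans ranking by |mean change| and by |t|. The third counts trials in which the hour ranked first by |mean change| differs from both others, using unadjusted 95% CIs.

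| True changes | Best hour picked | Winner separated from both |
|---|---|---|
| 0.4/0.5/0.4 | 51–63% | 2–3% |
| 0.3/0.5/0.3 | 70–86% | 5–14% |
| 0/0.5/0 | about 91% | 44–81% |

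When all hours are equal, the winner is separated in about 1% of trials. Ranking does well when one hour clearly stands out; the intervals tell the reader when that is so.

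**4. Criterion and measure.** With rho 0.5, largest |mean| and largest |t| pick different hours in about 8 to 21% of runs across all-equal, 0.3/0.5/0.3 and 0.4/0.5/0.4 patterns. This is with equal SDs, so unequal SDs are not covered. For six measures with between-measure correlation 0.5 to 0.9, rho 0.5 and ranking by |mean|, all six name the same hour in 22 to 60% of trials at 0.4/0.5/0.4, 43 to 72% at 0.3/0.5/0.3 and 71 to 86% at 0/0.5/0. Unanimity is a strict standard, and the simulation treats the measures as exchangeable although global CBF contains the regions.

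**5. The selected hour's estimate.** If all hours truly change by 0.30 SD, the selected hour averages 0.37 to 0.43. At 0/0.5/0 there is almost no net bias. Separation does not remove the bias: at 0.3/0.5/0.3 with rho 0.5 the mean error is +0.18 SD when the winner separates from both others and +0.06 SD when it does not. At 0/0.5/0 the non-separated trials understate, by 0.07 to 0.20 SD.

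**The case against.** **The repeated measures design already implies hour contrasts.** Such a model could produce them. But the Statistics section uses the phrase to explain that people are their own controls, and the comparisons it lists are with baseline. Being able to compute a contrast is not a plan to report it.

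**The three groups may be the three hours.** This is a fair reading: 1, 2 and 3 h is the only explicit set of three in the document, and E4 status has two levels. Even so, the sentence covers regional values only, is not linked to choosing an hour, and settles neither the criterion nor the deciding measure.

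**The criterion is not wholly open.** This stands in part. The Summary speaks of the best time for detecting a change, and the Statistics section refers to signal and noise. Both point to change relative to its variability. The fix should follow that lead.

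**It is a pilot, so ranking is enough.** This stands for picking an hour. It does not answer how firmly the data support the pick.

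A reader might infer more than the documents support:
- That the plan inflates type I error across hours. Three unadjusted tests would have a family-wise error of 11 to 14%, but the plan never says significance will choose the hour. That figure, like the 39 to 61%, applies only if it does.
- That the report would hide poor separation. The document contains no reporting plan, so it does not say that intervals will be omitted.
- That the selected change is always overstated, or only when the hours are not separated. Step 5 of the working contradicts both.

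**Conclusion.** The concern holds in a limited form. The choice required by objective 1 rests on comparisons with baseline, which cannot show that one hour is better than another, and the plan specifies no estimate of separation between hours. If significance is used and all hours truly change by 0.4 SD, an apparent distinction arises in about 39 to 61% of trials. This assumes change SD 1 and hour correlation 0.3 to 0.7; only n=30 comes from the documents, so the percentages show consequences under assumptions and are not findings about this trial.

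It does not follow that ranking is invalid or that the wrong hour will be named. The point should be fixed, because the remedy is nearly free and answers the stated objective better, but it does not undermine the study.

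**What to change.** Amend the Statistics section before analysis as follows.

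1. Analyse CBF at 0, 1, 2 and 3 h in one repeated-measures analysis. Alongside the three changes from baseline, report the 1 v 2, 1 v 3 and 2 v 3 h within-person differences with 95% CIs.
2. Name one deciding CBF measure in advance, for example global CBF with regions secondary.
3. State one criterion for the choice. Change relative to its variability is preferable, because the Summary frames the aim as detection.
4. Call the named hour provisional unless its 95% CIs against both other hours exclude zero.
5. Whether or not the hours separate, note that the selected hour's estimated change comes from the same 30 people used to select it and may be biased by the selection. Do not state a direction.

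The cost is SAP wording and a few lines of analysis, with no new scans or participants. There are three downsides. The chosen hour will usually be the same. The report will often have to say that n=30 does not separate the hours. An hour chosen on one measure may not be the best for a given region.
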